13.1.3.2 Mixed Model for Repeated Measures

Additionally, a mixed model repeated measures (MMRM) analysis will be conducted to further assess the primary endpoint. The MMRM will include the log-transformed change from baseline

value as the dependent variable with subject as random effect; time, randomized treatment group (0 = placebo, 1 = tildacerfont) and its interaction with time as fixed effects; as well as the log-transformed baseline serum DHEAS and age as a continuous covariates in the model. Within-subject correlations will be modeled using an unstructured covariance structure. Time ordering is a repeated measure within subjects. Errors for different subjects are assumed to be independent with an unstructured covariance structure. The p-value for testing the treatment effect from the MMRM model will be reported.

In the event the MMRM model with an unstructured covariance structure does not converge, the following covariance structures will be used as substitution in the order below. Each subsequent covariance structure will be used only if each previous covariance structure was used and the model did not converge.

1. Toeplitz covariance structure (assuming measurements from samples taken closer together in time are more highly correlated than those from samples taken farther apart)
2. First order of auto-regressive [AR(1)] covariance structure (assuming measurements from samples taken closer together in time are more highly correlated than those from samples taken farther apart)
3. Compound symmetry covariance structure (assuming equal correlation for measurements from a subject, regardless of how far apart in time when they were taken)

Subjects with missing data DHEAS data will not be imputed for the primary analyses.

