8.1. Sample Size Determination

A sample size of 33 subjects with 2:1 randomization will provide at least 80% power to detect a difference of 164 mcg/dL in mean DHEAS between at least one dose of tildacerfont and placebo assuming a standard deviation of 154 mcg/dL and a two-sided alpha of 0.05. Accounting for a 15% drop out, the final sample size is N=39 (n=26 for tildacerfont group and n=13 for placebo).

Subjects will be randomized using the strata of screening DHEAS ($\leq 1.2 \times \text{ULN}$, $> 1.2 \times \text{ULN}$).

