13 EFFICACY ANALYSES

The efficacy analyses are planned after all subjects have completed the 12 weeks of randomized, double-blinded study treatment and the database is frozen. During the 12 weeks of double-blind, placebo-controlled treatment period, the tildacerfont group will escalate doses at Week 4 and Week 8 to 100 mg QD and 200 mg QD, respectively. The scheduled visits included in this treatment period include Day 1 (baseline), Week 4, Week 8, and Week 12. The primary efficacy analysis will compare individual tildacerfont dose groups to the placebo group with respect to the change from baseline in serum DHEAS.

These efficacy analyses will be performed using the mITT Analysis Set ([Section 8.2](#)) as the main analyses. The endpoints identified in [Table 1](#) as the primary efficacy endpoint ([1.1](#)), secondary efficacy endpoint ([2.1](#)), and exploratory efficacy endpoints ([3.1](#), [3.2](#), [3.3](#), [3.4](#), [3.5](#), [3.6](#), [3.7](#), [3.8](#), [3.9](#)) will be analyzed.

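### The SAP's MMRM combines a random subject effect with an unstructured covariance, which is over-parameterised, and does not say which visit its single treatment p-value refers to

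*SAP*

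**What the plan says.** SAP 13.1.3.2 adds an MMRM to the primary ANCOVA. The model takes the log-transformed change from baseline "value as the dependent variable with subject as random effect". Its fixed effects are time, treatment (placebo or tildacerfont) and their interaction, with log baseline DHEAS and age as covariates. The same paragraph then states: "Within-subject correlations will be modeled using an unstructured covariance structure". If the unstructured model does not converge, the SAP moves in order to Toeplitz, AR(1) and compound symmetry. It does not say whether the random effect stays in those models.

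On reporting, 13.1.3.2 says: "The p-value for testing the treatment effect from the MMRM model will be reported". SAP 13.1.4.2 repeats this and adds geometric mean ratios and confidence intervals. Neither section names a visit or a contrast for the MMRM.

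The visits are set out in SAP 13: "The scheduled visits included in this treatment period include Day 1 (baseline), Week 4, Week 8, and Week 12". The active arm is on 50 mg up to Week 4, 100 mg up to Week 8 and 200 mg up to Week 12 (SAP 9.3.17), so visit and dose coincide. The primary estimand variable (13.1.1), the hypothesis (13.1.2) and the formal ANCOVA test (13.1.3.1) are all at Week 12. The ANCOVA section says explicitly that the model is then refitted at Weeks 8 and 4.

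**The concern.** There are two separate faults in one section.

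First, a random subject intercept adds the same constant to every element of the within-subject covariance matrix. An unstructured matrix is already free in every element, so the intercept variance cannot be separated from it. Non-convergence is the only stated trigger for leaving the unstructured model. A redundant parameter can itself produce non-convergence or a singular Hessian. The analysis could then move to a structure that forces equal variances at all visits because of how the model was written, not because of the data. SAP 13.1.5 repeats the MMRM in two subgroups, so the same wording governs still smaller data sets.

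Second, a model with treatment-by-time has no single treatment effect until a contrast is named. In most trials the average over visits is a mild choice. Here each visit is a different dose, so averaging changes the question, and the result could differ from the Week 12 analysis it is meant to support. Leaving the contrast open also leaves the analyst free to choose among several p-values after unblinding.

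**Working it through.** **1. The plan's own power figure.** Inputs from Protocol 8.1: "A sample size of 33 subjects with 2:1 randomization will provide at least 80% power", "to detect a difference of 164 mcg/dL in mean DHEAS", "assuming a standard deviation of 154 mcg/dL and a two-sided alpha of 0.05".

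- Placebo n = (1 + 1/2) × (1.960 + 0.842)² × (154/164)² = 1.5 × 7.85 × 0.882 = 10.4, rounded up to 11. That gives 11 + 22 = 33.
- Normal-approximation power at 22 versus 11 is 82.2%.
- Standard error = 154 × √(1/11 + 1/22) = 56.9. Noncentrality = 164/56.9 = 2.88. On 31 degrees of freedom the noncentral t power is 79.8%.
- Dropout: 33/0.85 = 38.8, rounded up to 39, which agrees with "Accounting for a 15% drop out, the final sample size is N=39".

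The stated figure is reproduced, to within rounding on the t calculation. About 80% is the benchmark for a Week 12 contrast below.

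**2. Covariance parameters.** Three visits give a 3 × 3 marginal covariance with 3 + 3 = 6 distinct elements. With residual matrix R, random-intercept variance u and J the matrix of ones, the marginal covariance is V = R + uJ. The rank of the derivative of V's distinct elements with respect to the parameters shows how many can be estimated.

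| Residual structure | Parameters alone (rank) | With random intercept (rank) | Identified with intercept? |
|---|---|---|---|
| Unstructured | 6 (6) | 7 (6) | No |
| Toeplitz | 3 (3) | 4 (3) | No |
| AR(1) | 2 (2) | 3 (3) | Yes |
| Compound symmetry | 2 (2) | 3 (2) | No |

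For the unstructured case, R can be replaced by V − uJ for any u that leaves it positive definite, and V is unchanged. For example, take V with variances 1, 1.1, 1.2 and covariances 0.5, 0.4, 0.6. Then u = 0, 0.1, 0.2 and 0.3 all give an admissible R and the same likelihood. The argument does not depend on the number of visits. Because V is the same, so are the treatment estimates whenever the fit is completed or u is fixed at zero.

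**3. Size of the contrast question.** The equal-weight main effect targets (d4 + d8 + d12)/3, where d4, d8 and d12 are the differences from placebo at Weeks 4, 8 and 12. With a common SD of 154 and correlation ρ between visits, the SD of a subject's mean over the three visits is 154 × √((1 + 2ρ)/3): 125.7 at ρ = 0.5 and 146.1 at ρ = 0.85. Take d12 = 164, 22 versus 11, and noncentral t on 31 degrees of freedom. The effect profiles and ρ are assumptions; the documents give neither.

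| Effect at Weeks 4 : 8 : 12 (fraction of 164) | Average effect, mcg/dL | Power, ρ = 0.5 | Power, ρ = 0.85 |
|---|---|---|---|
| 0 : 0.5 : 1 | 82.0 | 40% | 31% |
| 0.25 : 0.5 : 1 | 95.7 | 52% | 40% |
| 1/3 : 2/3 : 1 | 109.3 | 63% | 50% |
| 1 : 1 : 1 | 164.0 | 93% | 84% |

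Worked entry (third row, ρ = 0.5): 109.3/(125.7 × √(1/11 + 1/22)) = 109.3/46.4 = 2.36, giving 63%.

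The averaged test is the weaker one whenever the mean fraction falls below √((1 + 2ρ)/3), which is 0.82 at ρ = 0.5 and 0.95 at ρ = 0.85. Averaging therefore costs power when the effect rises with dose and gains power when it is flat.

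**The case against.** On the covariance, the rest of the paragraph describes an ordinary repeated-measures model, so the random subject effect may be loose wording for the subject block. The redundancy does not change which covariance matrices can be fitted, and nothing in the documents shows how likely non-convergence is. All of this stands. It limits the harm to an avoidable risk in fitting. It does not make the written model identifiable.

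On the p-value, a reader might infer that the SAP has chosen to average over the three doses in place of Week 12. The documents do not say so. SAP 13.1.4.2 uses the same phrase for the ANCOVA, which is fitted visit by visit. SAP 13 describes comparing individual dose groups with placebo. SAP 13.1.4.3 places the MMRM estimates in a section of plots over visits, which suggests by-visit estimates. Under reference coding, the treatment coefficient would be the effect at the reference visit, not an average. What stands against the plan is that the contrast is unnamed and that the usual default main-effect test is the average.

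A reader might also infer that the MMRM is bound to be less powerful. The flat profile contradicts that. Protocol 1.2.1 expects receptor occupancy of at most 50% at 50 mg and at least 90% at 200 mg, which makes a rising effect plausible. It also says that the occupancy needed to lower DHEAS is unknown.

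Finally, the MMRM is additional, the study is exploratory with no multiplicity adjustment (SAP 10.6), and the formal test is the ANCOVA. This is right, and it limits the weight of the point.

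**Conclusion.** The point holds as a specification fault in a supportive analysis. The unstructured model with a random intercept has one parameter too many at any number of visits (7 for 6 here). If the random effect is carried into the fallbacks, Toeplitz and compound symmetry are redundant too, and only AR(1) is identified. The consequence is nil if the redundant variance is set to zero. Otherwise the fallback sequence may be entered for a reason unrelated to the data; how often cannot be judged from the documents.

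The MMRM p-value has no stated visit. If the default main-effect test were used, power would be about 31–63% under the three rising profiles and 84–93% under equal effects, against about 80% for Week 12. These figures assume the planned 22 versus 11, the protocol's SD of 154 mcg/dL at every visit, equal correlations of 0.5–0.85, no covariate gain, and the untransformed scale of the sample-size statement, although the SAP analyses logs. SAP 15 records that the study was discontinued early with a small sample, so they show direction and rough scale only. The formal Week 12 ANCOVA test does not depend on any of this.

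**What to change.** In SAP 13.1.3.2, delete the phrase that makes subject a random effect and state that subject only identifies the block for the repeated measures, with visit as the repeated factor. Say that the same holds for each fallback structure. In 13.1.3.2 and 13.1.4.2, state that the MMRM p-value, geometric mean ratio and confidence interval are for the Week 12 treatment contrast, with the Week 8 and Week 4 contrasts reported separately.

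The cost is SAP wording only: no new data, no change in conduct and no change to the ANCOVA. After the change the unstructured model has 6 parameters and rank 6, and the MMRM addresses the same time point as the primary estimand. No change of estimation or degrees-of-freedom method is asked for here, since the point shows no error in either.

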13.1.4 Reporting Results

13.1.4.1 Summary of Descriptive Statistics

Descriptive statistics (8-point) for the serum DHEAS assessments, change from baseline in serum DHEAS, and % change from baseline in serum DHEAS will be presented by scheduled time point (i.e., Baseline [serum DHEAS only], Week 4, Week 8, and Week 12). For the baseline assessment only, the geometric mean and CV% will also be summarized.

If the normality assumption does not hold, the descriptive statistics of the change from baseline will be reported by treatment group and will include the median, the 95% distribution-free CI of the median, Q1, Q3, min and max.

13.1.4.2 Summary of Analysis Results

The p-value for testing the treatment effect from the (rank-based, if non-normal residuals) ANCOVA model will be reported. In addition, if the normality assumption holds, the back-transformed least squares (LS) GMR of change from baseline (post-baseline/baseline), two-sided 95% CI of the LS GMR, the back-transformed LS mean ratio difference between treatment group (i.e., tildacerfont/placebo), and 95% CI of the LS mean ratio treatment difference will be reported from the ANCOVA model. If the normality assumption does not hold, the difference of medians and its 95% CI will be reported. These values will be obtained from bootstrap method as the 50th percentile, the 2.5th percentile, and the 97.5th percentile, respectively, of the difference in group medians from 5000 bootstrap random samples drawn with replacement.

The p-value for testing the treatment effect from the (rank-based, if non-normal residuals) MMRM model will be reported. In addition, if the normality assumption holds, the back-transformed least squares (LS) GMR of change from baseline (post-baseline/baseline), two-sided 95% CI of the LS GMR, the back-transformed LS mean ratio difference between treatment group (i.e., tildacerfont/placebo), and 95% CI of the LS mean ratio treatment difference will be reported from the MMRM model.

13.1.4.3 Graph Presentation

A serial change from baseline in serum DHEAS plot will be presented using the mean change from baseline in a serum DHEAS. The y-axis will be the change from baseline level and the x-axis will represent the treatment visits: Baseline, Week 4, Week 8, and Week 12. All treatment groups will be presented on the graph. In addition, the LS GMR and the 95% CI from the MMRM model will be plotted.

For each treatment group, a spaghetti plot of all subjects' DHEAS levels over time (Baseline, Week 4, Week 8, and Week 12) will be plotted with the means at each time point overlaid. These spaghetti plots will be replicated for DHEAS change from baseline.

13.1.5 Subgroups

The above ANCOVA and MMRM analyses will be repeated for two separate subgroups: the subgroup of subjects who fully meet the inclusion criteria #3, and the subgroup of subjects that do not meet this criterion. Furthermore, the primary endpoint analyses will be descriptively summarized for the other subgroup(s) specified in [Section 10.8](#).

13.2 Secondary Efficacy Analysis

The secondary “treatment policy” estimand is the proportion of PCOS subjects with elevated androgens at baseline who were randomized into the study and achieved adequate control of serum DHEAS levels through the 12 weeks of double-blinded, placebo-controlled, dose-escalating Treatment Period. The active arm (dose escalation of tildacerfont from 50 mg QD to 100 mg QD to 200 mg QD) will be compared against the matching placebo group. The placebo treatment group will control for any potential placebo effects in PCOS subjects and their impact on the overall tildacerfont treatment effect. The superiority of tildacerfont is evaluated by comparing the proportion of tildacerfont subjects meeting this criterion is greater than the proportion of placebo subjects meeting this criterion.

Adequate control of serum DHEAS will be evaluated with two measurements: the proportion of subjects with a greater than 30% reduction from baseline and the proportion of subjects with $DHEAS \leq ULN$.

Population: The analysis population for the secondary efficacy analyses is the mITT analysis set, including all randomized PCOS subjects who received at least 1 dose of study drug (tildacerfont or placebo), have at baseline DHEAS assessment, and have at least one post-baseline DHEAS assessment.

Variable: The analysis variable is the proportion of subjects in the mITT analysis set who are responders (defined as [a] $\geq 30\%$ reduction in serum DHEAS or [b] $DHEAS \leq ULN$). This proportion is calculated for each treatment group (e.g., placebo, tildacerfont) as the number of subjects at each time point (Week 12, Week 8, Week 4) who have adequate control of serum hormones (greater than or equal to 30% reduction from baseline [\[2.1\]](#) or $DHEAS \leq ULN$ [\[2.2\]](#)),

divided by the total number of subjects in the mITT analysis who were randomized to that specific treatment.

Subjects with missing data are assumed to be non-responders. Subjects who do not have a 30% reduction from baseline (Objective 2.1) or subjects who have DHEAS > ULN (Objective 2.2) are considered non-responders.

The same analysis will be repeated for subjects with 25% and 20% reduction in DHEAS from baseline.

Intercurrent events: For the secondary analyses, intercurrent events such as treatment interruption or treatment discontinuation will be treated as non-responders, and use of prohibited medications will not be taken into consideration.

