3.1.2. Study Visits

Each subject will undergo a Screening Visit within 30 days of Day 1, three 4-week treatment periods, and a 30-day follow-up period. Subjects may also attend a DHEAS Screening Visit if needed (see [Section 3.1.2.1](#)). See the Schedule of Activities for full details of each study visit ([Section 12.2](#)).

Clinic visits should be scheduled for early in the morning to accommodate morning laboratory assessments (at 8 A.M. \pm 1 hour).

Sites will make scheduled telephone contacts to all subjects at Weeks 2, 6, and 10 to assess for the occurrence of any AEs and the initiation of new concomitant medications. The Early Termination Visit/Follow-up Visit may also be conducted by telephone at the discretion of the Investigator.

Subjects should be instructed to telephone sites if they have any concerns about their health and/or to report AEs.

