3.1.2.6. Early Termination Visit

Subjects who received any dose of study drug and discontinue study drug early or withdraw from the study will undergo an Early Termination Visit as soon as possible after the last dose of study drug. The Investigator will inquire about the reason for withdrawal and request the return of all unused study drug. Early termination assessments will occur as outlined in the Schedule of Activities ([Section 12.2](#)).

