8.3.4. Efficacy Analyses

All efficacy analyses will be conducted on mITT Population using a 2-sided alpha of 0.05. No adjustment for multiplicity is planned.

The primary endpoint, the change from baseline in DHEAS, will be used to evaluate the preliminary efficacy of tildacerfont therapy relative to placebo and will be summarized using an analysis of covariance (ANCOVA) model with baseline DHEAS as a covariate and randomization strata and dose level as independent variables. Each Treatment Period's final DHEAS assessment (ie, Week 4, Week 8, and Week 12) is the dependent variable. Additional covariates may be added in the SAP.

The proportion of subjects meeting specific DHEAS thresholds will be summarized using exact tests through logistic regression using a similar variable structure as the primary endpoint:

- DHEAS \geq 30% reduction from baseline vs <30% reduction from baseline
- DHEAS \leq ULN vs >ULN.

Additional covariates may be added in the SAP. Missing values for proportion endpoints will not be imputed and will be assumed to be failures.

Exploratory hormone and androgen endpoints will be summarized using an ANCOVA model using a similar variable structure as the primary endpoint. Additional endpoints may be specified in the SAP.

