5.2.2 Assessments

Appendix A: [Table 6](#) and [Table 7](#) show the schedule of events for the study.

5.2.2.1 Efficacy Hormone Assessments

The primary and secondary efficacy assessments are serum DHEAS. Exploratory efficacy assessments include adrenocorticotropic hormone (ACTH), dehydroepiandrosterone (DHEA), testosterone (T), androstenedione (A4), 17-hydroxyprogesterone (17-OHP), 11-ketoandrostenedione (11OHA4), 11 β -hydroxytestosterone (11OHT), 11-ketoandrostenedione (11KA4), and 11-ketotestosterone (11KT) will be measured. Efficacy hormone assessments will be collected Day 1, Week 4, Week 8, and Week 12 as shown in [Table 7](#).

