8.2 Modified Intent-To-Treat Analysis Set

The following modified ITT (mITT) Analysis Sets will include all randomized subjects who receive at least 1 dose of study drug (tildacerfont or placebo), have a baseline DHEAS assessment, and have at least one post-baseline DHEAS assessment. The mITT Analysis Set will be the basis for efficacy analyses.

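### The responder analyses score missing DHEAS as non-response, but the mITT denominator drops dosed subjects who leave before giving any post-baseline sample

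*SAP*

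**What the plan says.** SAP 13.2 defines the responder proportion at Weeks 12, 8 and 4 as the number of responders "divided by the total number of subjects in the mITT analysis who were randomized to that specific treatment". SAP 8.2 limits mITT to randomised subjects who took at least one dose, "have a baseline DHEAS assessment, and have at least one post-baseline DHEAS assessment".

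The missing-data rule points the other way. SAP 13.2 states "Subjects with missing data are assumed to be non-responders", and the indicator in SAP 9.3.12 (Table 3) is coded 0 when the value is missing. Protocol 8.3.4 says "Missing values for proportion endpoints will not be imputed and will be assumed to be failures". On stopping treatment, SAP 13.2 says that "intercurrent events such as treatment interruption or treatment discontinuation will be treated as non-responders".

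On sampling, SAP 5.2.2.1 states "Efficacy hormone assessments will be collected Day 1, Week 4, Week 8, and Week 12 as shown in" Table 7, and that table has no hormone draw in the early termination/follow-up column. Protocol 3.1.2.6 requires that subjects who stop early "will undergo an Early Termination Visit as soon as possible after the last dose of study drug", but Protocol 3.1.2 adds: "The Early Termination Visit/Follow-up Visit may also be conducted by telephone at the discretion of the Investigator".

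No responder analysis on the ITT set is planned. SAP 8.1 assigns that set to demographics and baseline characteristics.

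**The concern.** A change from baseline cannot be computed without a post-baseline value, so mITT is a natural set for the continuous endpoint. A responder indicator that codes missing as 0 needs no such value. For these endpoints the mITT condition only removes the subjects for whom the missing-equals-failure rule was written: those with no on-treatment result at all.

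Two subjects who both stop treatment can then be handled differently because of when they stopped. One who leaves in Week 3 without a sample is outside the denominator. One who gave a Week 4 sample and stops in Week 5 is inside it, as a non-responder at Weeks 8 and 12. The exclusion depends on an event after randomisation, and early loss may differ between arms, so it weakens the randomised comparison that failure imputation is meant to protect. It also sits badly with SAP 13.2 itself, which frames the secondary estimand in terms of randomised subjects.

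**Working it through.** **The plan's own figures.** Protocol 8.1 and SAP 7 give a difference of 164 mcg/dL, SD 154, two-sided alpha 0.05, 80% power and 2:1 allocation. Placebo n = (1.960 + 0.842)² × 154² × (1 + 1/2) / 164² = 10.4, rounded up to 11, so N = 33. Power at 22:11 is 82.2% by the normal approximation and 79.8% by the noncentral t. With 15% dropout, 33/0.85 = 38.8, rounded up to 39 (26:13). The stated 33 and 39 reproduce. Neither document gives a sample size, power or expected rates for the responder endpoints.

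**Who is removed.** Under SAP 5.2.2.1, Table 4 and Table 7:
- Leaves before Week 4, no later DHEAS: not in mITT, not scored.
- Leaves before Week 4, but a post-baseline sample is obtained: in mITT, non-responder through discontinuation.
- Week 4 sample, stops in Week 5: in mITT; the observed value counts at Week 4, and she is a non-responder at Weeks 8 and 12.
- Misses the Week 4 sample, stops in Week 5, gives none later: not in mITT, not scored.

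**Size of the distortion.** Removed subjects would all be non-responders under the plan's rule, so the numerator r does not change. With n dosed and a fraction q removed, the rate goes from r/n to r/(n(1-q)), a factor of 1/(1-q).

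Planned dropout is 0.15 × 26 = 3.9 on tildacerfont and 0.15 × 13 = 1.95 on placebo. The documents do not say how much of it falls before Week 4, so the range runs from none to all:
- tildacerfont, 0 to 4 removed: 26/26 to 26/22 = 1.00 to 1.18
- placebo, 0 to 2 removed: 13/13 to 13/11 = 1.00 to 1.18

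**Effect on the test.** Response counts are assumptions. The test is a two-sided Fisher exact test, which SAP 13.2.1.1 names as the fallback if the logistic model does not converge.

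Assumed responders 10 (tildacerfont) and 1 (placebo):

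| Removed, tildacerfont / placebo | Tildacerfont | Placebo | p |
|---|---|---|---|
| 0 / 0 | 10/26 = 38.5% | 1/13 = 7.7% | 0.063 |
| 1 / 0 | 10/25 = 40.0% | 1/13 = 7.7% | 0.060 |
| 2 / 0 | 10/24 = 41.7% | 1/13 = 7.7% | 0.057 |
| 3 / 0 | 10/23 = 43.5% | 1/13 = 7.7% | 0.031 |
| 4 / 0 | 10/22 = 45.5% | 1/13 = 7.7% | 0.027 |
| 3 / 1 | 10/23 = 43.5% | 1/12 = 8.3% | 0.055 |
| 0 / 1 | 10/26 = 38.5% | 1/12 = 8.3% | 0.121 |

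Assumed responders 12 and 2:

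| Removed, tildacerfont / placebo | Tildacerfont | Placebo | Difference (points) | p |
|---|---|---|---|---|
| 0 / 0 | 12/26 = 46.2% | 2/13 = 15.4% | 30.8 | 0.083 |
| 3 / 0 | 12/23 = 52.2% | 2/13 = 15.4% | 36.8 | 0.039 |
| 4 / 0 | 12/22 = 54.5% | 2/13 = 15.4% | 39.2 | 0.034 |
| 4 / 2 | 12/22 = 54.5% | 2/11 = 18.2% | 36.4 | 0.067 |
| 0 / 2 | 12/26 = 46.2% | 2/11 = 18.2% | 28.0 | 0.150 |

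In both sets p crosses 0.05 only when three or four tildacerfont subjects and no placebo subjects are removed. Loss on placebo alone moves the result against the drug.

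**The case against.** The strongest reply is that the gap depends on sampling. Any post-baseline DHEAS brings a subject into mITT, where discontinuation makes her a non-responder. The Protocol synopsis has DHEAS drawn at every clinic visit, which would cover an in-clinic Early Termination Visit. Protocol 6.1 foresees continued data collection where possible, and SAP 9.4 lets a sample from Days 15 to 43 fill Week 4. This stands as a limit on how often the problem arises. It does not close the gap, because SAP Table 7 shows no draw at that visit, the visit may be by telephone, and collection after stopping is best effort. A reader might infer that the defect persists whatever is sampled at early termination; the documents do not support that.

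A reader might also infer that the rule favours tildacerfont. The documents do not show this either. Early loss on placebo inflates the placebo rate, and nothing in them shows early intolerance on active drug; Protocol 1.2.2 describes the doses studied as generally well tolerated. A missing sample may also come from loss to follow-up, administrative withdrawal or a COVID-19 closure, so an excluded subject need not be a pharmacological failure. Under the plan's own rule she would still be scored as one.

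mITT is specified consistently for efficacy, and SAP 11.1.2 lists excluded subjects with reasons, so a reader could rebuild the denominator by hand. That helps transparency but does not change the planned test. The endpoints are secondary, in a study described as exploratory and without multiplicity adjustment, which limits the weight of the point.

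**Conclusion.** The concern holds in a conditional form. The plan's missing-equals-failure rule and its mITT denominator conflict for any dosed subject who leaves without a post-baseline DHEAS, and the schedule allows that to happen before Week 4. The size depends on how many such subjects there are and in which arm: a factor of 1.00 to 1.18 on an arm's rate if between none and all of the planned dropout falls early. A change in statistical significance needs frequent and one-sided early loss, and the examples rest on assumed response counts, the planned 26:13 split and the fallback test without covariates.

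SAP 15 reports that the study was discontinued early with a small sample. The actual denominators are therefore below 26:13, and each excluded subject weighs more than in the tables. If nobody was lost before giving a post-baseline sample, the results do not change.

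**What to change.** In SAP 13.2 and 9.3.12, for the 30%, 25%, 20% and ULN responder endpoints, define the denominator as all randomised subjects who took at least one dose and have a baseline DHEAS, and score absence of any post-baseline DHEAS as non-response. Baseline is needed for percent change, and the ULN model in SAP 13.2.1.1 also uses it as a covariate. For the ULN endpoint, keep the restriction in SAP Table 1, footnote 2, to subjects entering above ULN; SAP 10.8 and 15 indicate that some subjects did not.

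Cross-refer the exception in SAP 8.2 and 13, which now assign all efficacy analyses to mITT, and record the departure from Protocol 8.3.4 in SAP 15. Keep mITT for the continuous endpoint. Separately, reconcile the synopsis statement on DHEAS sampling with SAP Table 7 for the Early Termination Visit.

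The cost is a few short edits before database lock and no new data. Response rates fall slightly if anyone was lost early. Requiring one dose is still a condition applied after randomisation, but it no longer removes dosed subjects with a baseline value because their outcome is missing.
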